## 8.5 Administration of Investigational Product

At baseline, and as needed during the study, Investigational Product will be dispensed to randomized Subjects along with a diary. Each Subject will also receive written study instructions, which detail the proper application method of the Investigational Product and general study instructions.

Subjects will apply a thin layer of study medication to cover the entire face and other affected body areas once daily, avoiding contact with the mouth, eyes and open wounds. For the face applications subjects will be instructed to apply the product to the hand or cotton pad and gently rub it to the entire face. For the body applications (e.g., on the back, chest and shoulders), the product will be applied to the affected areas and gently rubbed into the skin. Subjects will wash their hands before and after administration of the Investigational Product. Investigational Product will be applied in this manner for 84 consecutive days.

Subjects will be required to use diaries to document the date of study treatments, any missed treatments and the occurrence of all adverse events. [*Redacted*].

Subjects will be instructed not to bathe, shower, wash or swim for at least 4 hours after the application of the Investigational Product.

At each visit during the study, the Investigator or designee should review proper application of the Investigational Product.

#### 8.6 Assessment of Compliance

Compliance with scheduled application of Investigational Product will be determined from the Subject's diary. The Subject will be instructed to use the diary to document all doses taken by checking the yes or no box for the appropriate date. In addition, Subjects will be instructed to document all AEs on the diary. Used Investigational Product will be returned to the study site at each scheduled visit or Early Discontinuation Visit. If the subject does not return the Diary, patient-reported dosing compliance will be recorded in the source notes and will be used to derive compliance between those visits.

#### 8.7 Investigational Product Accountability

It is the responsibility of the Principal Investigator to ensure that the current disposition of the Investigational Product is maintained at each study site where Investigational Product is inventoried and dispensed. When a drug shipment is received at a study site, the Principal Investigator or the Principal Investigator's Designee must inventory the drug and sign the receipt form provided with the shipment. The receipt form should be faxed to the drug depot as per instructions provided on the receipt. A copy of the receipt should remain at the site.

The Investigator will not supply study test articles to any person not enrolled in this study, or to any physician or scientist except those named as sub-investigators.

A Drug Accountability Log will assist study site staff in maintaining inventory records of study drug.

Subjects must return used, partially used or unused Investigational Product to the study site staff so that any remaining drug supplies can be accounted for and noted in the Drug Accountability Log. Weights of all dispensed units of the Investigational Product will be obtained before dispensing and after the units are returned to the study site.

The original Drug Accountability Log must be provided to the study monitor at the conclusion of the study and a copy should remain at the study site.

## 8.8 Retention of Study Drug Samples

A sufficient amount of the study drug will be randomly selected for retention by the packaging facility and shipped to the storage facility for a long term storage. [Redacted]

#### 8.9 Return of Clinical Supplies

All used and unused containers of Investigational Product may be returned to the Drug Labeling, Packaging and Shipping Facility for destruction or be destructed at the site after study close-out and final drug accountability is reconciled.

## 8.10 Additional Supplies Provided by The Sponsor

[Redacted]

## 9. STATISTICAL METHODS

## 9.1 Scientific and Statistical Considerations of the Study Design

The current study is designed to evaluate the safety and efficacy of this new formulation. Efficacy results will be used to calculate the sample size and establish endpoints for the Phase 3 studies.

The study was designed following FDA Guidance for Industry (Draft). Acne Vulgaris: Developing Drugs for Treatment. Division of Dermatologic and Dental Drug Products. FDA September 2005.

## 9.2 Sample Size Rationale

The primary statistical analyses of interest are the differences between the Test and the Placebo (Vehicle) treatments in the mITT population for mean inflammatory and non-inflammatory lesion count reductions, and for proportions of subjects with clinical success on the IGA for. In this Phase 2 study, approximately 300 Subjects will be enrolled to obtain at least 286 evaluable in the mITT Subjects (143 in each treatment group).

## 9.3 Randomization and Unblinding Procedures

Subjects will be randomly assigned in a 1:1 ratio to receive the test product or the vehicle (placebo) control. The randomization assignment will be generated using SAS® by an independent statistician, not involved with the study.

The Drug Labeling, Packaging facility will hold the randomization code throughout the conduct of the study in order to minimize bias. A sealed copy of the randomization scheme (as a scratch off portion of the product label attached to the drug accountability page) will be retained at the study site. In the event of an emergency, the Subject-specific treatment may be identified; however, every effort should be made to maintain the blind. Where possible, the CRO medical monitor should be contacted before breaking the blind for any patient. The Sponsor must be notified in the event the blind is broken.

The treatment assignments will remain blinded until the final database is closed.

## 9.4 Significance Level

All statistical tests will be two-sided at a significance level of  $\alpha$  = 0.05. No adjustment will be made for multiplicity.

## 9.5 Datasets to be Analyzed

Two analysis populations will be used in the analysis of the clinical data:

- 1. A safety population Subject is any individual who was randomized into the study and used at least one dose of investigational product.
- 2. The Modified ITT (mITT) population includes all Safety population Subjects who have met all inclusion/exclusion criteria and return for at least one post-baseline efficacy evaluation.

Efficacy analyses will be performed on the ITT. All efficacy data will be listed by treatment and Subject in data listings.

## 9.6 Handling of Missing Data

Missing safety data will not be imputed. In the analysis of efficacy on mITT population for subjects who discontinue from the study due to lack of efficacy, their IGA success endpoint will always be imputed as failure. In all other cases missing endpoints will be imputed with LOCF by carrying forward the last available post-baseline assessment.

## 9.7 Measures

Lesion Counts will be performed using the following definitions:

| Lesion Type        | Definition   |
|--------------------|--|
| Closed
Comedone | Non-inflammatory lesion; white, raised bumps caused by collections of oil and skin in pores. Also known as white heads and pimples         |
| Open
Comedone   | Non-inflammatory lesion; tiny, dark spots caused by a small plug in the opening of a follicle (pore) on the skin. Also known as blackheads |
| Papule             | Inflammatory lesion; raised spot on the skin that is less than 1 centimeter wide   |
| Pustule            | Inflammatory lesion; small, inflamed, pus-filled , blister-like lesions on the skin surface   |
| Nodules            | Large, hard bumps under the skin's surface   |
| Cysts              | A closed pocket or pouch of tissue. It can be filled with air, fluid, pus, or other material   |

| Definition of inflammatory | v and non-inflamatory | / lesions |
|----------------------------|-----------------------|-----------|
| Deminition of minaminatory | y and non-innamatory  |           |

The Investigator's Global Assessment (IGA) will be performed and documented using the definitions in the table, below:

| SA Scale for Ache Vulgaris |  |  |
|----------------------------|--|--|
| Grade                      | Description  |  |
| 0                          | Clear skin with no inflammatory or non-inflammatory lesions  |  |
| 1                          | Almost clear; rare non-inflammatory lesions with no more than one small inflammatory lesion  |  |
| 2                          | Mild severity; greater than Grade 1; some non-inflammatory lesions with no more than a few inflammatory lesions (papules/pustules only, no nodular lesions)    |  |
| 3                          | Moderate severity; greater than Grade 2; up to many non-inflammatory lesions and may have some inflammatory lesions, but no more than one small nodular lesion |  |
| 4*                         | Severe; greater than Grade 3; up to many non-inflammatory lesions and may have some inflammatory lesions, but no more than a few nodular lesions               |  |

## IGA Scale for Acne Vulgaris

\* The eCRF will allow for reporting of lesion worsening beyond Grade 4 with treatment. Subjects who worsen beyond Grade 4 will be described in the safety evaluation.

Please note that nodulocystic lesions will not be included in the inflammatory lesion count.

Counts of nodules and cysts will be reported separately and not included in the inflammatory or noninflammatory lesion counts

The following scale will be used for the application site reactions

[Redacted]

## 9.8 Demographics and Baseline/Randomization Characteristics

Demographic and baseline/randomization characteristics will be evaluated for comparability across treatment groups for the ITT and safety populations. [*Redacted*].

## 9.9 Safety Assessment

The extent of exposure will be summarized using descriptive statistics. No inferential analyses are planned.

Incidence of all adverse events reported during the study will be summarized using the MedDRA dictionary by treatment group, body system, severity, and relationship to study drug. The comparability of the Test and Placebo treatment groups for the frequency and severity of any adverse event that occurs in at least 5% of the Subjects in either treatment group will be evaluated using categorical methods.

Incidence of concomitant medications will be summarized by treatment group.

Safety analyses will be performed on the safety population. All safety data will be listed by treatment and Subject in data listings.

## 9.10 Efficacy Assessment

The efficacy assessment, superiority will be evaluated for each lesion type on the face using Analysis of Variance (ANOVA), with a statistical model containing terms for treatment and center, and with hypothesis testing at  $\alpha = 0.05$ . The analyses will evaluate if the mean percent change (reduction) from baseline, in each lesion type, for the Test treatment differs from that of the Vehicle. In case of extreme departure from the assumptions of normal error, defined as skewness of residuals from ANOVA model exceeding 2 in absolute value, a ranked-based, nonparametric method will be used. Superiority will be established If the

mean percent change (reduction) from baseline for the Test treatment, for each of the inflammatory and non-inflammatory lesion counts is greater than, and statistically different from (p<0.05), that for the Vehicle (Placebo) Control. For the proportions of subjects with treatment success on the IGA on the face the analysis will be evaluated by Fisher's exact test. Superiority will be established if the success proportion for the Test treatment is greater than, and statistically different from (p<0.05), that of the Vehicle.

In order to preserve an overall type-I error (alpha) of 5%, a hierarchical evaluation scheme will be employed. The comparisons of interest are:

- 1) percent change from baseline in the inflammatory lesion counts
- 2) percent change from baseline in the non-inflammatory lesion counts
- 3) proportions of subjects with treatment success on the IGA

These comparisons will be performed in sequence for weeks 12, 10, 8, 6, 4, and 2.

Statistical testing will begin with comparison 1. If statistical significance is attained with comparison 1 (p < 0.05), then a claim of superiority for comparison 1 can be made and the next comparison in the hierarchical evaluation scheme can be tested for statistical significance. If statistical significance is not attained for comparison 1 (p  $\ge$  0.05), then testing of all subsequent comparisons is stopped. The hierarchical, conditional-stepwise evaluation scheme allows for each comparison to be evaluated at the 5% level, while preserving an overall type I error rate of no more than 5%.

For **Subgroup** descriptive analyses comparing each lesion type and proportion of subjects with the treatment successon the body will be conducted for information purpose.

Efficacy results will be used to calculate the sample size for the Phase 3 studies.

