## Statistical Methods:

#### Efficacy Analyses

The efficacy assessment, superiority will be evaluated for each lesion type on the face using Analysis of Variance (ANOVA), with a statistical model containing terms for treatment and center, and with hypothesis testing at  $\alpha = 0.05$ . The analyses will evaluate if the mean percent change (reduction) from baseline, in each lesion type, for the Test treatment differs from that of the Vehicle. In case of extreme departure from the assumptions of normal error, defined as skewness of residuals from ANOVA model exceeding 2 in absolute value, a ranked-based, nonparametric method will be used. Superiority will be established If the mean percent change (reduction) from baseline for the Test treatment, for each of the inflammatory and non-inflammatory lesion counts is greater than, and statistically different from (p<0.05), that for the Vehicle (Placebo) Control. For the proportions of subjects with treatment success on the IGA on the face the analysis will be conducted using two-sided,  $\alpha = 0.05$  Fisher's exact test. Superiority will be established if the success proportion for the Test treatment is greater than, and statistically different from (p<0.05), that of the Vehicle.

In order to preserve an overall type-I error (alpha) of 5%, a hierarchical evaluation scheme will be employed. The comparisons of interest are:

- 1. percent change from baseline in the inflammatory lesion counts
- 2. percent change from baseline in the non-inflammatory lesion counts
- 3. proportions of subjects with treatment success on the IGA

These comparisons will be performed insequence for weeks 12, 10, 8, 6, 4, and 2.

Statistical testing will begin with comparison 1. If statistical significance is attained with comparison 1 (p < 0.05), then a claim of superiority for comparison 1 can be made and the next comparison in the hierarchical evaluation scheme can be tested for statistical significance. If statistical significance is not attained for comparison 1 (p ≥ 0.05), then testing of all subsequent comparisons is stopped. The hierarchical, conditional-stepwise evaluation scheme allows for each comparison to be evaluated at the 5% level, while preserving an overall type I error rate of no more than 5%.

For **Subgroup** descriptive analyses comparing each lesion type and proportion of subjects with the treatment success on the body will be conducted for information purpose.

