At Visit 1, an informed consent/assent and HIPAA authorization will be obtained from the potential study Subject before any study procedures take place. After the Subject has been consented/assented, the Subject's medical history will then be documented, including the Subject's concomitant medications. A urine pregnancy test will be performed for female Subjects of childbearing potential. All female Subjects are considered to be of childbearing potential unless they are premenarchal, have been surgically sterilized or have been postmenopausal for at least 1 year. A baseline acne grade will be assigned to the Subject using the Investigator's Global Assessment (IGA) and a baseline lesion count will be performed. The Subject will undergo a brief physical examination, including the recording of vital signs. The Subject will be evaluated for signs and symptoms of local irritation. The Subject will be reviewed against the inclusion/exclusion criteria. Blinded Investigational Product will be dispensed to Subjects who meet all of the inclusion and exclusion criteria using the lowest patient randomization number available at that investigative site. Subjects will be instructed on the application of Investigational Product and completion of Subject diaries. The Investigational Product should not be opened in the clinic. The first application of Investigational Product will be reviewed.

Subjects will return to the study site for visits at Weeks 2, 4, 6, 8, 10, and 12. The Subject's concomitant medications will be reviewed and documented. A urine pregnancy test will be performed for female Subjects of childbearing potential. The Subject will be evaluated for signs and symptoms of local irritation and any adverse events will be documented. The Subject's facial acne will be assessed using the IGA, the Subject's lesions will be counted and these results will be documented. The Subjects are instructed to bring their used Investigational Product and their study diaries to each study visit. Compliance with drug applications will be assessed at each visit. Additional units of Investigational Product will be dispensed and each Subject will receive new diaries during visits at Weeks 2, 4, 6, 8, and 10. In addition, all Investigational Product and diaries will be collected from the Subject during each scheduled visit or the Early Discontinuation Visit.

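### IGA success is tested by a conservative, unstratified Fisher's exact test and the lesion-count model leaves out baseline count: valid tests, but some power is given up

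*Combined protocol and SAP*

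**What the plan says.** - **IGA success.** Section 9.10: "the analysis will be evaluated by Fisher's exact test". The synopsis (Efficacy Analyses) names the same test and adds "the analysis will be conducted using two-sided"; Section 9.4 likewise has "All statistical tests will be two-sided at a significance level of" 0.05. No stratum is named in any of these places. The success criterion is one of direction plus significance: "Superiority will be established if the success proportion for the Test treatment is greater than, and statistically different from" vehicle at p<0.05.
- **Lesion counts.** Percent change from baseline in each lesion type is analysed by ANOVA "with a statistical model containing terms for treatment and center". The fallback applies to an extreme departure from normality, "defined as skewness of residuals from ANOVA model exceeding 2 in absolute value"; then "a ranked-based, nonparametric method will be used". The rank method and its covariates are not named.
- **Baseline data.** Section 3, for Visit 1: "A baseline acne grade will be assigned to the Subject using the Investigator's Global Assessment (IGA) and a baseline lesion count will be performed". The visit schedule and Section 7.1 agree.
- **Endpoint and entry.** The synopsis defines success as a fall of at least 2 IGA grades. Section 4.1 admits grades 2, 3 and 4.
- **Size.** Section 9.2 plans about 300 enrolled, to give at least 286 evaluable (143 per arm). It states no power, effect, SD or response rate.

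The model and test sentences in Section 9.10 and the synopsis carry no redaction.

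**The concern.** Both baselines enter the definitions of the endpoints, but neither is used to remove variation between subjects when the arms are compared. This has three parts.

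1. Fisher's test conditions on both margins and is discrete, so its true size lies below 5%, and the shortfall costs power.
2. A subject entering at grade 2, 3 or 4 must reach 0, 1 or 2 to be a success. Entry grade may therefore predict success, and it is ignored. The documents do not say whether it does, or in which direction.
3. Percent change may still be correlated with baseline count. If so, leaving the count out keeps avoidable residual variance.

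At stake is the chance of showing a real effect on the endpoints that Section 9.2 calls the analyses of primary interest. Under the hierarchy in Section 9.10 a miss also stops all later tests.

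**Working it through.** **Inputs from the documents:** two-sided alpha 0.05 (9.4); 143 per arm, 286 in total (9.2); about 5 centers and entry grades 2 to 4 (4.1). The 286 cannot be reproduced, because no power, effect, SD or rates are stated. All success rates, grade mixes, odds ratios and correlations below are therefore assumptions, shown as ranges. All powers are for a test taken on its own, outside the hierarchy.

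**1. Fisher against uncorrected Pearson chi-square (exact).** Power = Σ over rejected tables (x, y) of Bin(x; 143, p_Test) × Bin(y; 143, p_Vehicle). Size is the same sum with equal rates.

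| Common success rate | 5% | 10% | 20% | 30% |
|---|---|---|---|---|
| Fisher size | 2.4% | 3.2% | 3.5% | 3.7% |
| Chi-square size | 4.8% | 4.9% | 5.0% | 5.0% |

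| Vehicle v Test | Fisher power | Chi-square power | Loss (points) |
|---|---|---|---|
| 15% v 27% | 65.8% | 71.0% | 5.2 |
| 10% v 25% | 90.2% | 92.8% | 2.6 |
| 15% v 35% | 97.0% | 97.9% | 0.9 |

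For vehicle success of 5, 10, 15, 20 and 30%, the Test rate was solved to give a fixed chi-square power, and Fisher's power was read at the same rates:

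| Chi-square power | 70% | 80% | 90% | 95% |
|---|---|---|---|---|
| Fisher loss (points) | 4.2–6.7 | 3.4–5.5 | 2.2–3.5 | 1.4–2.1 |

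**2. Further effect of stratifying by grade (simulated).** CMH without continuity correction was compared with chi-square in 40,000 runs per scenario (Monte Carlo SE about 0.25 points), at odds ratio 2.

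| Vehicle success by grade 2/3/4 | Grade mix | CMH minus chi-square (points) |
|---|---|---|
| Grade not prognostic | – | -0.6 (65.0 to 64.4%) |
| 8/15/22% | 20/65/15% | +0.3 |
| 3/15/35% | 20/65/15% | +3.0 |
| 3/15/35% | equal | +6.0 |
| 35/15/3% | equal | +6.0 |

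The last two rows show that the direction of the grade effect does not matter. At odds ratio 3 the range is -0.1 to +3.5.

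Total gain of CMH over Fisher across these scenarios:

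| Odds ratio | Fisher power | Gain (points) |
|---|---|---|
| 2 | 49–59% | +5.1 to +11.8 |
| 2.5 | 75–86% | +2.8 to +10.1 |
| 3 | 90–97% | +0.9 to +5.8 |

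*Size of CMH* (200,000 runs in each of ten null scenarios, SE about 0.05 points): 4.8–5.0% at overall success of 5–30%, 4.45–4.74% at 2–2.5%, and 2.35% at 1%.

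*Agreement of test and estimate.* In stratum g, with a of n1 successes on Test, b of n0 on Vehicle, m = a + b and N = n1 + n0, the CMH numerator term is a − n1·m/N = (n1·n0/N)(a/n1 − b/n0). The numerator is thus the Mantel-Haenszel-weighted sum of the stratum risk differences. The weighted risk difference always has its sign.

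**3. Lesion counts.** Adjusting for baseline divides the standardised effect by √(1 − r²), where r is the within-arm correlation of percent change with baseline count. Degrees of freedom: 286 − (1 + 1 + 4) = 280 without baseline, 279 with it. With 280 df, 143 per arm detects about 0.33 SD at 80% power. The equivalent number of extra subjects is 286/(1 − r²) − 286.

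| Assumed r | 0.09 | 0.14 | 0.17 | 0.30 |
|---|---|---|---|---|
| 80% power becomes | 80.3% | 80.8% | 81.1% | 83.6% |
| 90% power becomes | 90.2% | 90.6% | 90.8% | 92.5% |
| Extra subjects | 2.3 | 5.7 | 8.5 | 28.3 |

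Count data were also simulated with assumed entry limits (5,000 runs; SE 0.7 points for power). ANOVA to ANCOVA power went from 55.0 to 55.3% at |r| 0.08 and from 51.9 to 53.1% at |r| 0.16. Size was 4.7–5.1% for both models. The skewness rule fired in 26–34% of these runs, so the form of the rank model matters.

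**The case against.** - **Nothing is broken.** A pre-specified exact test is a legitimate choice, and no planned power is missed because none is stated. This stands. It is why the point is an improvement and not an error.
- **IGA is third in the hierarchy, so stand-alone losses overstate the effect.** This stands in part. If each count test had 80% power and the tests were independent, the 5.2-point loss becomes 5.2 × 0.8 × 0.8 = 3.3 points in the chance of claiming IGA at week 12, and the 2.6-point loss becomes 1.7. The loss is smaller but still there.
- **The grade effect is unknown, and the top of the range needs a steep assumed gradient.** True of the size of the gain. But CMH beats Fisher even when grade is not prognostic, so the case for changing the test does not rest on it.
- **The count gain is close to nil.** Possibly. Percent change already uses baseline, and in one simulation with r near zero ANCOVA lost 0.6 points. The eligibility criteria are redacted, so r cannot be settled.
- **Stratifying by grade ignores center.** So does the planned Fisher test. Crossing center with grade can be too fine: in one assumed scenario it lowered power from 77.3% (center strata only) to 75.8%.
- **Fisher's guarantee of size is given up, and a rank difference replaces a mean difference when the fallback applies.** Both are real costs. The first is small by the simulated sizes. The second is implicit in the plan's own rank fallback, which leaves it unstated.

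**Conclusion.** The concern holds as a point of efficiency. Each planned test, taken singly, is valid; there is no bias and no inflation of type I error.

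The firm part is Fisher's conservatism: true size of 2.4–3.7% at success rates of 5–30%, and a loss of 3.4–5.5 points where chi-square power is 80%, falling to 1.4–2.1 at 95%. The size figures are exact for 143 per arm. The power figures depend on assumed rates. Stratifying by grade adds between -0.6 and +6.0 points at odds ratio 2, depending on unknown prognostic strength and grade mix. The baseline count is probably the smallest gain. Because the data are already collected, the change should be made, but the trial does not fail without it. Confidence is medium, since the documents give no rates, SD, target power or grade mix.

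**What to change.** Pre-specify before unblinding, in Section 9.10 and the synopsis, for every week tested:

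> Percent change in each lesion type will be analysed by ANCOVA with treatment, center and the baseline count of the same lesion type. The skewness rule applies to the residuals of this model; if it is met, the same model will be fitted to ranked percent change and ranked baseline count. Superiority requires p<0.05 and an adjusted treatment difference (of ranks, if the rank model applies) favouring Test. IGA success will be compared by a two-sided Cochran-Mantel-Haenszel test without continuity correction, stratified by baseline IGA grade. Superiority requires p<0.05 and a stratified risk difference (Mantel-Haenszel weights, reported with 95% CI) favouring Test. Fisher's exact test is a sensitivity analysis.

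**Cost.** It needs a change to the analysis text and no new data or visits. CMH relies on a large-sample approximation, whereas Fisher guarantees size at or below 5%. CMH is itself conservative when successes are very rare, as may happen at early weeks. If grade is not prognostic, stratifying costs about 0.6 points against chi-square. ANCOVA uses one degree of freedom.
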